#### **2. Endpoint events that will be unblinded**

There is a subset of SAEs, which will require unblinding and expedited reporting to competent authorities/relevant ECs and investigators, if these meet SUSAR and/or endpoint criteria and are indicative of one of the following events:

- Fatal events, which are often associated with drug toxicity and which include SAEs indicative of anaphylaxis, angioedema, blood dyscrasias (including agranulocytosis, aplastic anemia, bone marrow failure, pancytopenia and bicytopenia), hepatic injury, inflammatory lung disorders (including allergic, fibrosing, necrotizing alveolitis, eosinophilic pneumonia and interstitial lung disease), rhabdomyolysis, and serious

cutaneous skin reactions (including Stevens-Johnson syndrome, toxic epidermal necrolysis and erythema multiforme) torsade de pointes and prolonged QT interval.

- Efficacy endpoints, for which the investigator considers that the character and the severity of the endpoint is not consistent with the expected presentation or course of that endpoint and the investigator considers that the study drug and/or study procedures may have contributed to this abnormal presentation.

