### **Study-specific unblinding rules for SUSARs that are commonly observed in the study population**

In clinical trials evaluating treatments for high morbidity and/or high mortality disease states, SAEs that are known consequences of the underlying disease or condition under investigation, or events common in the study population, are anticipated to occur with some frequency during the course of the trial, regardless of drug exposure. While the investigator must still report all non-serious AEs and SAEs through Day 5, and Day 14, respectively, SUSARs considered consistent with the following SAE Preferred Terms will not be unblinded and reported in an expedited timeframe to regulatory agencies, ECs or investigators during the course of the study:

abdominal pain, acute coronary syndrome, acute pulmonary oedema, anaemia, angina pectoris \*, anxiety, arthralgia, asthenia, azotaemia, back pain, blood creatinine \*, blood pressure \*, blood urea nitrogen \*, bronchitis \*, cardiac arrest, cardiac arrhythmias (all Preferred Terms presenting any type of arrhythmia *excluding* electrocardiogram QT interval abnormal, electrocardiogram QT prolonged, long QT syndrome, torsade de pointes), cardiac asthma, cardiac failure \*, cardiac output \*, cardiac pacemaker \*, cardiac tamponade, cardiogenic shock, cardiorenal syndrome, cerebrovascular accident, chest pain, chronic obstructive pulmonary disease, confusional state, constipation, cor pulmonale \*, cough \*, creatinine renal clearance \*, delirium, diarrhea, dizziness, dyspnea \*, ejection fraction \*, fatigue, generalized oedema, glomerular filtration rate \*, gout, headache, hepatic congestion, hyperglycemia, hyperkalemia, hyperlipidemia, hypertension \*, hyperuricaemia, hypoglycemia, hypokalemia, hypernatremia, hypotension \*, implantable defibrillator \*, influenza \*, insomnia, loss of consciousness, muscle spasm, musculoskeletal pain, myocardial infarction\*, nasopharyngitis, nausea, oedema, oedema due to cardiac disease, oedema peripheral, osteoarthritis, pain in extremity, pericardial effusion, pleural effusion, pneumonia \*, presyncope, pulmonary hypertension, pulmonary oedema, renal failure \*, renal impairment, respiratory distress \*, respiratory failure \*, respiratory tract infection \*, stroke\*, syncope, transient ischemic attack, urinary tract infection, valve \*, ventricular failure \*, vomiting, weight increased

\*More than one PT can contain this term.

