Detailed AE listings will also be provided.

In addition, AEs representing identified and potential safety risk in addition to events of interest will be grouped. The incidence (absolute and relative frequency) of each potential risk will be summarized by treatment group. Odds ratios and associated 95% confidence intervals comparing serelaxin with placebo will be presented using the Mantel-Haenszel test. In addition, subjects experiencing each of these risks will be listed. Such safety risks and events of interest are displayed in below table.

Table 2-7 Safety risk and event of interest search specification

Type of Risk	Specification
Safety risk	
Hypotension	Search terms include the following PTs: Blood pressure ambulatory decreased Blood pressure decreased Blood pressure diastolic decreased Blood pressure immeasurable Blood pressure orthostatic decreased Blood pressure systolic decreased CT hypotension complex Diastolic hypotension Dizziness postural Hypotension Mean arterial pressure decreased Neonatal hypotension Orthostatic hypotension Procedural hypotension Altered state of consciousness Blood pressure abnormal Blood pressure ambulatory abnormal Blood pressure diastolic abnormal Blood pressure fluctuation Blood pressure inadequately controlled Blood pressure orthostatic abnormal Blood pressure systolic abnormal Blood pressure systolic inspiratory decreased Consciousness fluctuating Depressed level of consciousness Dizziness Dizziness exertional Labile blood pressure Loss of consciousness Presyncope

Type of Risk	Specification
	Schellong test
	Syncope
	Tilt table test positive
Hemoglobin/ hematocrit transient decrease	SMQ 'Haemorrhages' (Broad) HLGT 'Anaemias nonhaemolytic and marrow depression'
Fetotoxicity and Teratogenicity	SMQ 'Haematopoietic erythropenia' (Broad) SMQ 'Pregnancy and neonatal topics' (Broad)
Event of interest	
Hypokalemia	Search terms include the following PTs: Alkalosis hypokalaemic Blood potassium abnormal Blood potassium decreased Hypokalaemia Hypokalaemic syndrome Hyperkaliuria Transtubular potassium gradient Urine potassium abnormal Urine potassium decreased Urine potassium increased
Menorrhagia/Metrorrhagia	HLGT 'Menstrual cycle and uterine bleeding disorders'
Potential promotion of cancers	SMQ 'Malignancies' (Broad)

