Immunogenicity/Hypersensitivity	SMQ 'Hypersensitivity' (Broad) SMQ 'Angioedema'(Broad) SMQ 'Anaphylactic reaction'(Broad) SOC 'Immune system disorders' HLGT 'Immunology and allergy investigations' HLGT 'Administration site reactions' SMQ 'Severe cutaneous adverse reactions'(Broad)
Cardiac failure	SMQ 'Cardiac failure' (Broad)
QT prolongation	SMQ 'Torsade de pointes/QT prolongation' (Broad) SMQ 'Cardiac arrhythmias' (Broad)
Thromboembolic events	SMQ 'Embolic and thrombotic events'
Renal impairment	SMQ 'Acute renal failure' (Broad)
Respiratory failure	SMQ 'Respiratory failure' (Broad)
Hepatotoxicity	SMQ 'Drug related hepatic disorders – comprehensive search' (Broad)

AEs with an onset between informed consent and study drug initiation will be listed.

For each AE listed, the verbatim term and PT, the corresponding severity, relationship to study drug, seriousness (yes/no), and start and stop date and time of the event will be specified and displayed by treatment group and subject number.

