2.5 Sample size and power considerations

The alpha (α) level of 5% is split to CV death at 4% and to WHF at 1%. The sample size calculation is based on the CV death endpoint. This is an event-driven trial with fixed maximum duration of 180 day follow-up period for each patient. In the sample size calculation, the 180-day CV death rate is assumed to be 9.0% in the placebo group, which is about 80% of 11.3% of all cause death observed in the placebo group in the RELAX-AHF study.

The interim analysis will be performed when 329 CV deaths are accrued. At the interim analysis, if Z-score of 2.786 (one-sided nominal $p = 0.0027$) is observed, which corresponds to HR of 0.735 (at least 26.5% RRR), the DMC may recommend to stop the study due to crossing the boundary. If there is no stopping at the formal efficacy interim analysis, the final analysis will need to have a Z-score of 2.072 (one-sided nominal $p = 0.0192$), which corresponds to HR of 0.838 (at least 16.2% RRR), to declare a significant study. ([contact], Cytel Inc., Cambridge MA, 2010).

If the observed overall event rate of the CV death endpoint during the course of the trial is much lower than expected based on the design assumptions (assessed on a blinded basis), adjustments may be made to the number of patients to be randomized in order to achieve the required number of events in the pre-planned timeframe (180 days) and thus to preserve the target study power.

For the sample size of 6,800, the unconditional power for the WHF endpoint and all three key secondary endpoints under various HRs (mean difference for Length of Stay) are summarized in the tables below:

Table 2-10 Assumed effect sizes for worsening heart failure and the key secondary efficacy variables on power calculation

	Assumed HR or mean difference
Worsening Heart Failure (placebo rate: 12.2%)	0.70
	0.80
All cause death (placebo rate: 11.3%)	0.80
	0.816
	0.83
Length of Stay (mean ±SD between placebo and serelaxin: 0.9 ±9.6 day)	0.9 day
	0.7 day
CV death or HF/RF rehospitalization (placebo rate: 34.1%)	0.85
	0.88

Note: Assumed placebo rates for all cause death and WHF and mean difference (mean + SD) in LOS between serelaxin and placebo were based on RELAX AHF study; placebo event rate of CV death or HF/RF rehospitalization was estimated to be 34.1% by assuming an exponential distribution with the same hazard as that observed through Day 60 in RELAX AHF study.

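### The SAP's QT prolongation event of interest is pooled with all cardiac arrhythmias, so its odds ratio would mainly reflect background arrhythmia

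*SAP*

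**What the plan says.** SAP Section 2.3.1 states that "AEs representing identified and potential safety risk in addition to events of interest will be grouped", with an incidence by treatment group for each risk. It adds: "Odds ratios and associated 95% confidence intervals comparing serelaxin with placebo will be presented using the Mantel-Haenszel test". Patients with each risk are also listed.

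Table 2-7 gives the searches. For QT prolongation it names "SMQ 'Torsade de pointes/QT prolongation' (Broad) SMQ 'Cardiac arrhythmias' (Broad"). Both are in the broad version. No row carries the label cardiac arrhythmias, and no row uses the torsade/QT search by itself.

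Protocol Section 7.2 deals with these terms for another purpose, the unblinding and expedited reporting of suspected unexpected serious reactions. It describes a class of "events common in the study population, are anticipated to occur with some frequency during the course of the trial, regardless of drug exposure". The list that follows includes "cardiac arrhythmias (all Preferred Terms presenting any type of arrhythmia", and excludes from that entry "electrocardiogram QT interval abnormal, electrocardiogram QT prolonged, long QT syndrome, torsade de pointes". The same section, under endpoint events that will be unblinded, places "torsade de pointes and prolonged QT interval" among fatal events often linked to drug toxicity.

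**The concern.** An odds ratio for a pooled category is driven by its commonest component. If ordinary arrhythmias are much more frequent than QT or torsade terms, as the protocol's description of them as background suggests, a row labelled QT prolongation mostly compares arrhythmia between the arms.

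This can mislead in two directions. A real excess of QT or torsade terms on serelaxin would appear as an odds ratio close to 1. Conversely, a drug effect on ordinary arrhythmia, harmful or protective, would be reported as an effect on QT. In both cases the estimate does not measure what its label says. What is at stake is the interpretation of one safety output. No primary or key secondary analysis is involved.

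**Working it through.** The plan states no expected rate, odds ratio or power for this event group, so there is no figure of its own to reproduce. The check asks how much dilution follows from the definition.

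**Inputs from the documents.** The pooled definition and the odds ratio come from SAP Section 2.3.1. The planned size comes from SAP Section 2.5 ("For the sample size of 6,800"), with 1:1 allocation in Protocol Section 3.1, so about 3,400 per arm are randomized.

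**Assumptions.** The Safety Set has 3,300 patients per arm. QT/torsade terms occur in q0 = 0.2% on placebo and q1 = 0.6% on serelaxin. Other arrhythmia terms occur at the same rate a in both arms, independently of QT terms. The rate a is varied from 0.5% to 10%.

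**Formulas.**
- Pooled risk in an arm: p = 1 − (1 − q)(1 − a).
- Odds ratio: OR = [p1/(1 − p1)] / [p0/(1 − p0)].
- Approximate 95% CI: exp(ln OR ± 1.96 × SE), with SE = √[1/(n·p0) + 1/(n(1 − p0)) + 1/(n·p1) + 1/(n(1 − p1))] (Woolf, unstratified).

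**QT terms alone.** Expected patients are 3,300 × 0.002 = 6.6 and 3,300 × 0.006 = 19.8. OR = (0.006/0.994)/(0.002/0.998) = 3.01. SE = 0.450, so the CI is 1.25 to 7.28.

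**Pooled, worked at a = 5%.** p0 = 1 − 0.998 × 0.95 = 0.0519 and p1 = 1 − 0.994 × 0.95 = 0.0557. OR = (0.0557/0.9443)/(0.0519/0.9481) = 1.08. SE = 0.109, so the CI is 0.87 to 1.33.

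| Background arrhythmia, both arms | Pooled risk, placebo vs serelaxin | QT share of placebo events | Expected OR (95% CI) |
|---|---|---|---|
| none (QT alone) | 0.20% vs 0.60% | 100% | 3.01 (1.25–7.28) |
| 0.5% | 0.70% vs 1.10% | 29% | 1.58 (0.93–2.66) |
| 1% | 1.20% vs 1.59% | 17% | 1.34 (0.88–2.02) |
| 3% | 3.19% vs 3.58% | 6% | 1.13 (0.86–1.47) |
| 5% | 5.19% vs 5.57% | 4% | 1.08 (0.87–1.33) |
| 10% | 10.18% vs 10.54% | 2% | 1.04 (0.89–1.22) |

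The QT share is q0/p0.

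**Sensitivity to the QT assumptions.** With 3,400 per arm, placebo QT rates from 0.1% to 0.5% and background arrhythmia from 2% to 10%, a true QT odds ratio of 2 appears as 1.01 to 1.20, and one of 3 as 1.02 to 1.40. QT terms make up half or more of the placebo events only if other arrhythmias are no commoner than QT terms.

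**Cancellation.** At a = 5%, the pooled odds ratio equals exactly 1 if arrhythmia on serelaxin falls to a1 = 1 − (1 − 0.0519)/(1 − 0.006) = 4.62%. That is a relative fall of (5 − 4.62)/5 = 7.6%, small enough to arise by chance.

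**The case against.** Four objections deserve weight.

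*QT findings are visible elsewhere.* A reader might infer that a QT signal would be hidden in the trial, or that this row is the only summary of QT risk in treated patients. The documents do not support that. SAP Section 2.3.1 tabulates all adverse events by system organ class and preferred term, adds tables by severity, drug relation and discontinuation, and lists the patients with each risk. About 7 versus 20 patients could be read from the preferred-term table if they were coded to the few QT terms. The ECG substudy (SAP Section 2.3.4, at least 500 patients) gives corrected QT thresholds and changes from baseline. This objection stands and limits the point to one odds ratio. The compensation is partial: the preferred-term table spreads QT terms over several lines without a combined QT odds ratio, and the substudy covers about 7% of patients (500/6,800).

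*The protocol does not contradict the SAP.* A reader might take Protocol Section 7.2 as stating the opposite of Table 2-7. It is a rule on unblinding and expedited reporting and does not prescribe analysis groupings, so the two can coexist. Its relevance is only that it regards arrhythmia as background and QT terms as distinct.

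*The rates are assumed.* This is true. Neither document gives QT or arrhythmia adverse event rates or the contents of the searches. The direction of the bias needs only that other arrhythmias outnumber QT terms; its size depends on the assumed rates. One should not lean on atrial fibrillation here, because its mention in the entry criteria shows presence at randomization, not new events after the infusion starts.

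*Component results may be intended.* SAP Section 2.3.7.1 mentions a standard table by search and preferred term for hepatotoxicity. If the same layout were used for QT, the problem would shrink, but Section 2.3.1 does not say so. Other rows also combine several searches, and no decision rule is attached to these odds ratios. In the extracted text one nearby row appears to have slipped, so the printed table should be checked, although no stray arrhythmia label is visible.

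**Conclusion.** The point holds in a limited form. As written, the QT prolongation odds ratio pools QT/torsade terms with all cardiac arrhythmias. It would be pulled toward 1 for a QT effect whenever other arrhythmias are commoner than QT terms, and it would label an arrhythmia effect as a QT effect.

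Under the illustrative rates, a threefold QT odds ratio shrinks to about 1.6 even at 0.5% background arrhythmia, and to between 1.13 and 1.04 at 3% to 10%. These sizes rest on assumed rates, an equal arrhythmia rate in both arms, and one pooled estimate being produced for the row. Severity is minor to moderate: the label and the estimate do not match, but the underlying QT data remain visible in other planned outputs.

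**What to change.** In SAP Table 2-7, define QT prolongation by the torsade/QT search alone. Add cardiac arrhythmias as its own event of interest, defined by its own search. In Section 2.3.1, give each row its own incidence and odds ratio. The pooled row may be kept as an extra under a label that names both components. If results by component search were always intended, one sentence in Section 2.3.1 saying so would be enough.

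The cost is one more output row. No additional data are needed, and no alpha or primary analysis changes. The QT row will contain fewer events and have a wider interval, as the 1.25 to 7.28 in the illustration shows, but it will estimate what its label says.

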2.3.2 Laboratory data

2.3.2.1 Hematology and chemistry

In addition to local laboratory evaluations for all randomized subject, a laboratory substudy will be conducted at a subset of selected sites to enroll at least 1600 subjects. Subjects without written informed consent for the laboratory substudy before any study-specific assessment is performed will be excluded from the population.

Descriptive summaries of actual and change from baseline will be presented for all continuous clinical laboratory values by treatment and time point.

Clinical shift tables showing the pattern of change from baseline versus each post-baseline time point will be presented based on the cross-classification of the number of subjects with clinical laboratory values below (low), within (normal), or above (high) normal ranges for each laboratory test.

All laboratory data will be listed for each subject. Laboratory values that are outside the normal ranges will be flagged high (H) or low (L).

The number and percentage of subjects with clinically notable laboratory results, including categorical analysis on laboratory parameters of interest after baseline will be presented. Clinically notable laboratory values are defined in protocol Appendix 1. The notable laboratory values related to liver function are detailed in [Section 2.3.7](#).

The data from local and central laboratory will be presented separately.

2.3.2.2 Creatinine and eGFR changes

eGFR will be calculated according to simplified Modification of Diet in Renal Disease (sMDRD).

The proportion of subjects with > 0.3 mg/dL increase, >0.5 mg/dL increase, > 1.0 mg/dL increase and >50% increase from baseline in serum creatinine levels at each time point, and at any time point, will be presented.

The proportion of subjects with decreases from baseline GFR of >25%, >40%, >50%, and >30 mL/min/1.73 m² at each time point, and at any time point, will be presented.

The data from local and central laboratory will be presented separately.

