### **2.2 Key and other secondary objectives**

#### **Key secondary objectives**

- To demonstrate that serelaxin is superior to placebo in reducing all-cause mortality during a follow-up period of 180 days
- To demonstrate that serelaxin is superior to placebo in reducing the length of total hospital stay during the index AHF hospitalization
- To demonstrate that serelaxin is superior to placebo in reducing the composite endpoint of CV death or rehospitalization due to heart failure/renal failure, during a follow-up period of 180 days

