f At screening, a locally-analyzed sample will be obtained for female patients of child-bearing potential to qualify the patient for study entry.

g Chest X-ray may be interpreted by the study physicians or physicians attending to the patient. Interpretation and the person interpreting the radiograph must be recorded in the source documentation. A radiologist’s interpretation is not necessary for the purposes of the study.

h A complete physical will be performed at screening; an abbreviated physical examination will be performed at all other specified timepoints. Following randomization, all physical examinations should be performed daily at approximately the same time of day. Daily vital signs measurements may be made and recorded by trained study personnel as well as trained healthcare personnel as part of their routine clinical duties. The first recorded measurement per day will be used as the daily measurement for that day. Refer to [Section 6.5.1](#).

 BP and HR measurements are to be performed at 30 & 60 minutes and then every hour for the first 6 hours of study drug infusion, and then every 3 hours during study drug infusion, including night time hours. Post-infusion, BP and HR are to be measured every 3 hours until 12 hours following end of infusion, then every 6 hours for 48 hours and then every 24 hours until the earlier of Day 5 or Discharge. All measurements should be performed as close as possible to specified timepoints. BP and HR are to be measured with the patient in the same position and with the same equipment using the same arm, throughout study drug infusion. These measurements may be made and recorded by trained healthcare personnel as part of their routine clinical duties, as well as trained study personnel. Refer to [Section 6.5.2](#).

j Blood will be locally collected and analyzed daily during hospitalization. If discharge occurs prior to Day 5, local blood collection will not be required at the Day 5 hospital/clinic visit. Following randomization, local laboratory collections can be adjusted to conform to the hospital's routine laboratory collection schedule and can be collected at any time of day. Refer to [Section 6.5.4](#).

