### **6.5.4 Laboratory evaluations**

A local laboratory will be used for analysis of all specimens collected. The laboratory name and value must be entered into the eCRF page. Local laboratory specimens will be collected at Screening, daily while hospitalized up to Day 5 and at discharge. Following randomization, local laboratory collections can be adjusted to conform to the hospital's routine laboratory collection schedule and can be collected at any time of day.

Laboratory values that exceed the boundaries of a notable laboratory abnormality should be assessed for AEs and additional evaluations should be performed, as judged appropriate by the investigator. If the laboratory abnormality induces clinical signs and symptoms, or requires therapeutic intervention, then the diagnosis or medical condition must be entered on the AE screen of the patient's eCRF. If the laboratory abnormality is the primary reason for an unforeseen hospitalization or otherwise fulfills the seriousness category of an AE, then the procedure for immediate notification of SAEs must be followed. Likewise, if the laboratory abnormality leads to discontinuation from the study, then the patient must be followed until the abnormality resolves or is judged to be permanent.

In addition to the local laboratory collections outlined above, at least 1600 patients from selected centers will participate in a laboratory substudy. A central laboratory will be used for the analysis of all baseline and post-baseline specimens collected in the subset of patients participating in the laboratory substudy. Central laboratory specimens will be collected at baseline (can be collected at screening), daily while hospitalized up to Day 5, at Discharge, Day 5 if discharged prior to Day 5, and Day 14. Following randomization, central laboratory collections can be adjusted to conform to the hospital's routine laboratory collection schedule and can be performed at any time of day. Details of the substudy are described in [Section 6.5.4.3](#).

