#### **6.5.4.2 Clinical chemistry**

The following serum chemistry tests will be measured locally at screening and daily during hospitalization: sodium, potassium, glucose, blood urea nitrogen (BUN) or urea, AST, ALT,

alkaline phosphatase, total bilirubin, and creatinine. In addition, BNP/NT pro-BNP and hemoglobinA1c will be measured at screening only.

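### Local any-time creatinine and eGFR proportions depend on length of stay, so a shorter stay on serelaxin would modestly favour it

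*SAP*

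**What the plan says.** SAP 2.3.2.2 sets four creatinine thresholds (rises above 0.3, 0.5 and 1.0 mg/dL, and above 50%) and four for falls in eGFR. The proportion of patients with a given "increase from baseline in serum creatinine levels at each time point, and at any time point, will be presented". The section adds: "The data from local and central laboratory will be presented separately". It gives no common observation window, no denominator rule and no allowance for the number of samples per patient.

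For all patients, Protocol 6.5.4 states: "Local laboratory specimens will be collected at Screening, daily while hospitalized up to Day 5 and at discharge". The local-laboratory footnote to Protocol Table 6-1 adds: "If discharge occurs prior to Day 5, local blood collection will not be required at the Day 5 hospital/clinic visit". Protocol 6.5.4.2, whose list includes creatinine, has no Day 5 limit: "The following serum chemistry tests will be measured locally at screening and daily during hospitalization".

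For the substudy, Protocol 6.5.4 says that "at least 1600 patients from selected centers will participate in a laboratory substudy". Its central samples are taken at baseline, daily in hospital to Day 5, and then "at Discharge, Day 5 if discharged prior to Day 5, and Day 14".

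One of the key secondary objectives (Protocol 2.2) is: "To demonstrate that serelaxin is superior to placebo in reducing the length of total hospital stay during the index AHF hospitalization".

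**The concern.** An any-time proportion rises with the number of times a patient is sampled. Here that number depends on the discharge date, which treatment may change. If serelaxin patients leave earlier, they are sampled less often, and fewer rises are found even when the true risk is equal. The local by-visit proportions have a related weakness: on the later days they come mainly from patients still in hospital, a group formed after randomization.

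No other rule in the SAP repairs this. The discharge-visit mapping in SAP 2.1.3 relabels an existing value and adds no sample. The missing-data rules in SAP 2.2.9 cover efficacy only.

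The direction matters. Patients are selected for an eGFR of 25 to 75 mL/min/1.73m², and Protocol 3.6 already suggests that the drug protects the kidney. A small reduction produced by sampling could be read as support for that view.

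**Working it through.** **1. The plan's own figure for stay.** The documents give no expected creatinine or eGFR proportions. They do give power for length of stay: 93% for 0.9 day and 78% for 0.7 day (SAP Table 2-11, WHF HR 0.7 and composite HR 0.85). Inputs are 6,800 patients at 1:1, so 3,400 per arm, and SD 9.6 days (SAP Table 2-10). I take one-sided alpha as 0.0125, half of 0.025, as the share for stay once both primaries are rejected. The graph is not shown, so that share is an assumption.
- Standard error = 9.6 × √(2/3400) = 0.2328.
- 0.9 day: 0.9/0.2328 − 2.241 = 1.624, power 94.8%.
- 0.7 day: 0.7/0.2328 − 2.241 = 0.765, power 77.8%.

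Both are within 2 points of the stated values, so 0.7 to 0.9 day is the difference the plan works with.

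**2. The mechanism by hand.** With k independent samples, each with probability q of a rise, the any-time proportion is 1 − (1 − q)^k. At q = 5%, five samples give 22.6% and four give 18.5%. Real samples are correlated, and the average loss is less than one sample, so the true effect is smaller.

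**3. Who leaves before Day 5.** The documents give no mean stay. Assume a lognormal stay with mean 8 and SD 9.6 days:
- s² = ln(1 + (9.6/8)²) = 0.892, so s = 0.944; μ = ln 8 − 0.446 = 1.633.
- Placebo: P(stay < 5) = Φ((1.609 − 1.633)/0.944) = 49%.
- Serelaxin, every stay 0.9 day shorter: P(placebo stay < 5.9) = Φ((1.775 − 1.633)/0.944) = 56%.

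About 51% and 44% would then still be in hospital at Day 5.

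**4. Simulation with no renal effect.** Both arms have identical creatinine paths; only stay differs. Assumptions, none from the documents: mean stay 6, 8 or 10 days; stay shortened by 0.7 or 0.9 day, as a constant or in proportion; baseline creatinine about 1.4 mg/dL; between- and within-patient SD of log creatinine 0.10 and 0.10 with autocorrelation 0.6, or 0.15 and 0.12 with 0.8. Results for an any-time rise above 0.3 mg/dL, with mean stay 8 days, a constant 0.9-day shift and the smaller SDs:

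| Schedule | Placebo | Serelaxin | Difference (points) | Ratio |
|---|---|---|---|---|
| Local (daily to Day 5, plus discharge) | 18.3% | 16.5% | 1.75 | 0.90 |
| Central substudy | 23.9% | 23.2% | 0.73 | 0.97 |
| Fixed days for everyone (1–5 and 14) | 23.5% | 23.5% | 0 | 1.00 |

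The mean number of local samples per patient falls from 4.63 to 4.15. Over all settings, the local difference is 0.3 to 2.4 points (ratio 0.87 to 0.985) and the central difference 0.1 to 0.9 points (ratio 0.96 to 0.996). If local draws continue daily beyond Day 5, as Protocol 6.5.4.2 can be read, the local difference is 0.9 to 2.6 points.

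**5. Against sampling error.**
- Local example: √((0.183 × 0.817 + 0.165 × 0.835)/3400) = 0.92 point, so 1.75 points is 1.9 standard errors.
- Smallest local case (20.48% v 20.16%): 0.32/0.98 = 0.3 standard error.
- Largest local case (20.76% v 18.35%): 2.41/0.96 = 2.5 standard errors.
- Central example at 800 per arm: √((0.239 × 0.761 + 0.232 × 0.768)/800) = 2.1 points, against a difference of 0.73.

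A simpler model assumes daily risks of 10, 8, 6, 5 and 5%, 4% at discharge, and a stay 0.7 to 1.0 day shorter. It gives 0.6 to 1.0 point, against a standard error of √(2 × 0.28 × 0.72/3400) = 1.1 points.

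**The case against.** A reader might infer that renal safety as a whole is biased, or that serelaxin will look safer only because fewer samples are drawn. The documents support neither. SAP 2.3.2.2 already reports central results separately, and those include Day 5 and Day 14 samples after discharge. The SAP also has a grouped renal-impairment event (2.3.1), a repeated-measures analysis of cystatin C at Days 2, 5 and 14 (2.2.7.3), and adjudicated rehospitalization for heart or renal failure through Day 180 (2.2.6.3). The bias arises only if stay differs, and a true renal effect could coexist with it. The tables are descriptive and carry no alpha.

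The size can also be challenged. Length of stay is scored to Day 60, and in-hospital deaths receive the maximum plus one day, so a mean difference of 0.9 day may come from long stays rather than from discharges before Day 5, where most local samples are lost. Both models make creatinine risk independent of discharge; if discharged patients are at lower risk, the bias is smaller.

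These points stand, and they limit the concern to one set of tables. They do not remove it. The local data are the only creatinine data on all patients; the substudy is at least 1,600 of about 6,800 (1600/6800 = 24%), at selected centers. Its daily draws also stop at discharge, and the footnotes to Protocol Table 6-1 allow telephone contact for patients who do not return.

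**Conclusion.** The concern holds in a limited form. The local any-time creatinine and eGFR proportions depend on length of stay. If serelaxin shortens the stay, they will be modestly biased in its favour, by roughly 0.3 to 2.4 points. That is often within one to two standard errors, and about 2.5 in the most extreme setting. The later local by-visit proportions describe mainly patients still in hospital. Central results are less affected (0.1 to 0.9 point) but not immune.

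The dependence on stay follows from the documents. The size does not: it rests on assumed stay and creatinine distributions and on a stay difference not yet shown in this trial. No power or error rate changes. This is a worthwhile low-cost improvement rather than a flaw in the trial's main conclusions.

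**What to change.** In SAP 2.3.2.2, before unblinding, keep the existing tables and make these additions:
- a local any-time proportion restricted to a common window through Hour 48, used as the between-arm local comparison;
- a central-laboratory summary limited to the fixed Day 5 and Day 14 visits;
- denominators and number of samples per patient, by arm, in every table;
- a label on the unrestricted local any-time result saying that it depends on length of stay.

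Protocol 6.5.4 (daily draws up to Day 5) should be reconciled with Protocol 6.5.4.2 and the Table 6-1 footnote (daily during hospitalization), so that it is clear which local values count. The same label would suit the notable post-baseline values in SAP 2.3.2.1, for which no size was calculated.

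All samples are already planned, so the cost is SAP wording and a few more tables. The Hour 48 window misses later worsening. The Day 5 and Day 14 comparisons are less precise: at a 28% event rate and 800 per arm, the standard error is √(2 × 0.28 × 0.72/800) = 2.2 points, against 1.1 for the whole trial.

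The window also does not guarantee independence from stay. The lognormal in step 3 puts Φ((0.693 − 1.633)/0.944) = 16% of placebo and Φ((1.065 − 1.633)/0.944) = 27% of serelaxin patients out before Hour 48. Entry requires an expected 48 hours of intravenous therapy, so real figures should be lower, but this is why sample counts by arm are needed.
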